APPENDIX C

COMPOSITE TUMOR RESPONSE CRITERIA FOR PATIENTS WITH LOCALLY ADVANCED BASAL CELL CARCINOMA

For all patients with locally advanced basal cell carcinoma (BCC), externally visible target lesions will be chosen by the investigator *and* must include any lesions that are both externally visible and measurable according to the Response Evaluation Criteria in Solid Tumors (RECIST). The externally visible component of all target lesions should be at least 10 mm in the longest dimension, to facilitate accurate and reproducible measurement. Standardized digital photographs of the externally visible component of all target lesions must be obtained at baseline and at the time of each tumor assessment (see Appendix H). For patients with a target lesion that contains both an externally visible and a RECISTmeasurable component, appropriate imaging studies (computed tomography or magnetic resonance imaging) will be used to assess the RECIST component of tumor response (see Appendix B). Investigators must also provide a clinical description of the target lesion(s) at baseline and at each tumor assessment, as well as comments on any changes in the lesion(s) since the previous assessment.

All patients will undergo baseline and on-study biopsies of target lesions per Appendix G; in patients achieving a clinical response, histologic analysis of on-study biopsies will be used for final determination of complete versus partial response (see below).

Clinical Response Criteria (for all patients with locally advanced BCC)

A. Externally Visible Tumor Dimension

The externally visible component of target lesion(s) will be measured in the longest dimension at each tumor assessment and will be documented using standardized digital photography. If the border of the tumor is no longer visible but a scar is present, the dimensions of the scar should be measured.

Response criteria for tumor dimension are as follows:

- Complete Response (CR): *all* target lesion(s) no longer visible, maintained for at least 4 weeks
- Partial Response (PR): decrease of 30% or greater in the sum of the longest dimension of target lesion(s), maintained for at least 4 weeks
- Stable Disease (SD): not meeting criteria for CR, PR, or progressive disease (PD)
- Progressive Disease (PD): increase of ≥ 20% in the sum of the longest dimension of target lesion(s)

B. Tumor Ulceration (only for patients whose target lesion[s] are ulcerated at baseline)

Response criteria are as follows:

- CR: re-epithelialization of the entire baseline area of ulceration of target lesion(s), maintained for at least 4 weeks
- PR: there are no criteria for PR
- SD: not meeting criteria for CR or PD
- PD: new ulceration of target lesion(s), not related to (i.e., in a location separate from) tissue biopsy or other known trauma, persisting without evidence of healing for at least 2 weeks

| Overall Clinical Responses for All Possible Combinations of Tumor Responses for Locally Advanced BCC | | | |
|---|-------------------------------------|--------------------------|-----------------------|
| Externally Visible Tumor Dimension | Tumor Ulceration (If Applicable) | New Lesions ^a | Clinical Response |
| CR or PR | Non-PD | No | Response ^b |
| SD | CR | No | Response ^b |
| SD | SD | No | SD |
| PD | Any | Any | PD ° |
| Any | PD | Any | PD ° |
| Any | Any | Yes | PD ° |

CR = complete response; PD = progressive disease; SD = stable disease.

^a See above for definitions.

^b In patients achieving clinical response, histologic analysis of biopsies will be used for final determination of CR vs. PR; see below and Appendix G.

^c If the investigator's assessment of progressive disease is equivocal, and in the investigator's opinion the patient is still deriving benefit from treatment, treatment with CX-4945 should be continued, and the patient should be re-evaluated at the next tumor assessment timepoint.

Clinical plus RECIST (for patients with locally advanced BCC whose target lesion[s] have both externally visible and RECIST-measurable components)

See Appendix B for RECIST; also see Section C above with respect to the criteria for new skin lesions.

| Clinical Response | RECIST | Clinical + RECIST |
|--------------------------|----------|-----------------------|
| | Response | Response |
| Response | Non-PD | Response ^a |
| SD | CR or PR | Response ^a |
| SD | SD | SD |
| PD | Any | PD ^b |
| Any | PD | PD ^b |

CR = complete response; PD = progressive disease; PR = partial response;

RECIST = Response Evaluation Criteria in Solid Tumors; SD = stable disease.

^a In patients achieving clinical response, histologic analysis of biopsies will be used for final determination of CR vs. PR; see below and Appendix G.

^b If the investigator's assessment of progressive disease is equivocal, and in the investigator's opinion the patient is still deriving benefit from treatment, treatment with CX-4945 should be continued, and the patient should be re-evaluated at the next tumor assessment timepoint.

In patients with a clinical response, histologic analysis of biopsies will be used for final determination of CR (absence of residual BCC) versus PR (residual BCC present); see Appendix G.

In addition, if all previously inoperable target lesions are rendered operable with clear margins obtained at the time of surgery, this will be considered a PR. If the investigator deems a previously inoperable lesion to be potentially operable, the Medical Monitor should be consulted prior to any surgical procedure

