10.1.2. Exclusion Criteria

Patients who meet the following criteria will be excluded from study entry:

- 1. Pregnant or nursing women. NOTE: Women of child-bearing potential and men must agree to use adequate contraception (hormonal or barrier method of birth control; or abstinence) prior to study entry and for the duration of study participation. Should a man father a child, or a woman become pregnant or suspect she is pregnant while participating in this study, he or she should inform the treating physician immediately.
- 2. Concurrent non-protocol-specified anti-tumor therapy (e.g., chemotherapy, other targeted therapy, radiation therapy, or photodynamic therapy)

- For patients with multiple cutaneous BCCs at baseline that are not designated by the investigator as target lesions, treatment of these non-target BCCs with surgery may be permitted but must be discussed with the Medical Monitor prior to any surgical procedure.

- For patients with locally advanced BCC whose target lesion(s) is/are inoperable at baseline but is/are later deemed potentially operable because of tumor response to CX-4945, surgery with curative intent may be permitted but must be discussed with the Medical Monitor prior to any surgical procedure.

- 3. History of other malignancies within 3 years of Day 1, except for tumors with a negligible risk for metastasis or death, such as adequately treated squamous-cell carcinoma of the skin, ductal carcinoma in situ of the breast, or carcinoma in situ of the cervix.
- 4. Active or uncontrolled infections or with serious illnesses or medical conditions which would not permit the patient to be managed according to the protocol.
- 5. History of other disease, metabolic dysfunction, physical examination finding, or clinical laboratory finding giving reasonable suspicion of a

disease or condition that contraindicates use of an investigational drug or that might affect interpretation of the results of the study or renders the patient at high risk from treatment complications.

- 6. Difficulty with swallowing oral medications.
- 7. Chronic diarrhea (excess of 2-3 stools/day above normal frequency).

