- b. A complete physical exam includes evaluation of the head, eyes, ears, nose and throat; cardiovascular, dermatological, musculoskeletal, respiratory, gastrointestinal, and neurological systems.
- c. Vital signs include pulse, systolic and diastolic blood pressure while the patient is in a seated position, respiratory rate, and temperature.
- d. Tumor assessments must be performed at screening and every 8 weeks thereafter. Assessments should include an evaluation of all sites of disease. Patients in the metastatic BCC cohort will undergo tumor assessments per the Response Evaluation Criteria in Solid Tumors (see Appendix B). Patients in the locally advanced BCC cohort will undergo tumor assessments per the composite tumor response criteria (see Appendix C).
- e. Instructions for obtaining digital photographs are given in Appendix H.
- f. For patients with locally advanced BCC, a baseline tumor biopsy must be performed in accordance with guidelines (see Appendix G). Perform biopsy again on Week 8. Repeat biopsy either at best clinical response if achieved prior to Week 24 or at Week 24. A tumor biopsy is recommended at the time of progression.
- g. Hematology consists of hemoglobin, hematocrit, platelet count, red blood cell (RBC) count, white blood cell (WBC) count, and percent or absolute differential count (neutrophils, eosinophils, lymphocytes, monocytes, basophils, and other cells).
- h. Serum chemistry includes glucose, blood urea nitrogen (BUN), creatinine, sodium, potassium, magnesium, bicarbonate, calcium, total protein, albumin, total bilirubin, alkaline phosphatase, AST, and ALT.
- i. Urinalysis includes pH, specific gravity, glucose, protein, ketones, and blood.
- j. Measurement of serum 25-hydroxyvitamin D (25[OH]D or calcidiol) is required at screening. Follow-up 25(OH)D measurements will be performed every three months. Patients found to have serum 25-hydroxyvitamin D (25[OH]D) concentration lower than 20 ng/mL during the screening period should receive vitamin D supplement.
- k. For women of childbearing potential, including those who have had a tubal ligation. A serum pregnancy test is required at screening and urine pregnancy tests will be performed at specified subsequent visits. If a urine pregnancy test is positive, it must be confirmed by a serum pregnancy test.

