3.2. Response Criteria

3.2.1. Evaluation of target lesions. This section provides the definitions of the criteria used to determine objective tumor response for target lesions. The criteria have been adapted from the original WHO Handbook, taking into account the measurement of the longest diameter only for all target lesions:

Complete Response—the disappearance of all target lesions; Partial Response at least a 30% decrease in the sum of the longest diameter of target lesions, taking as reference the baseline sum longest diameter; Progressive Disease—at least a 20% increase in the sum of the longest diameter of target lesions, taking as reference the smallest sum longest diameter recorded since the treatment started or the appearance of one or more new lesions; Stable Disease—neither sufficient shrinkage to qualify for partial response nor sufficient increase to qualify for progressive disease, taking as reference the smallest sum longest diameter since the treatment started. If the investigator's assessment of progressive disease is equivocal, and in the investigator's opinion the patient is still deriving benefit from treatment, treatment with CX-4945 should be continued, and the patient should be re-evaluated at the next tumor assessment timepoint.

3.2.2. Evaluation of nontarget lesions. This section provides the definitions of the criteria used to determine the objective tumor response for nontarget lesions: complete response—the disappearance of all nontarget lesions; incomplete response/stable disease—the persistence of one or more nontarget lesion(s); and progressive disease—the appearance of one or more new radiographically identified lesions and/or unequivocal progression of existing nontarget lesions. A new radiographically identified lesion is defined as a lesion that has not previously been seen in prior imaging studies, and that has increased in size to either a diameter larger than the size of the slice thickness being used for that imaging modality or at least 5 mm, whichever is larger.

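### Appendix C has no progression rule for existing non-target skin BCCs without a RECIST-measurable component, so their growth can coexist with a scored Response or SD

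*Protocol*

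**What the plan says.** **Target selection.** Appendix C states that "externally visible target lesions will be chosen by the investigator". The same sentence limits the choice: the targets "must include any lesions that are both externally visible and measurable according to the Response Evaluation Criteria in Solid Tumors (RECIST"). Inclusion criterion 5 asks for at least one lesion of 10 mm or more on a photograph. No provision makes every such lesion a target.

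**Scoring.** Partial response on dimension is a "decrease of 30% or greater in the sum of the longest dimension of target lesion(s), maintained for at least 4 weeks". PD on dimension is an increase of at least 20% in that same target sum. PD on ulceration is "new ulceration of target lesion(s), not related to" biopsy or other known trauma. The clinical response table combines target dimension, target ulceration and new lesions. Its title claims to cover every combination, and a new lesion is always PD.

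**Non-target lesions elsewhere in the documents.**
- Exclusion criterion 2 expects them: "For patients with multiple cutaneous BCCs at baseline that are not designated by the investigator as target lesions", surgery may be permitted after discussion with the Medical Monitor.
- Flowchart footnote d (Appendix A) says "Assessments should include an evaluation of all sites of disease" but attaches no scoring rule.
- RECIST in Appendix B does have a non-target PD rule, "unequivocal progression of existing nontarget lesions", and a non-target column in its Table 1. Its scope is imaged disease in non-skin organs or subcutaneous disease.
- SAP 11.9.1 repeats the composite and adds nothing on non-target lesions.

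**The concern.** A visible BCC that was present at baseline, was not chosen as a target and has no RECIST-measurable component is neither a target nor a new lesion. Whatever it does, no row of the Appendix C table responds. The protocol foresees such lesions and asks for all sites to be evaluated, so the information may be seen at the visit and still have no effect on the score.

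The table is also uneven. A new skin lesion makes the patient PD, but unequivocal growth of an old one does not.

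The score feeds ORR, complete response rate, PFS, duration of response, duration of stable disease, disease control rate and duration of disease control in the locally advanced cohort (SAP 11.9 and 11.10). The study is open-label, and the investigator both selects the targets and scores the response, so the rule should not leave this case open.

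**Working it through.** **1. Trace one patient through the rules.** Lesion sizes are assumptions chosen for illustration. The target shrinks from 40 to 26 mm: (26 − 40)/40 = −35%, which meets the 30% criterion. It is assumed to be maintained for 4 weeks, with no ulceration PD and no new lesion. A second, purely cutaneous BCC of 30 mm at baseline is not a target.

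| Second lesion at assessment | Its own change | Appendix C as written | Change if both were summed (baseline 70 mm) | Score if both were summed |
|---|---|---|---|---|
| 30 mm | 0% | Response | (26 + 30 − 70)/70 = −20.0% | SD |
| 36 mm | +20% | Response | (26 + 36 − 70)/70 = −11.4% | SD |
| 45 mm | +50% | Response | (26 + 45 − 70)/70 = +1.4% | SD |
| 60 mm | +100% | Response | (26 + 60 − 70)/70 = +22.9% | PD |
| 90 mm | +200% | Response | (26 + 90 − 70)/70 = +65.7% | PD |

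The summed score becomes PD at 1.2 × 70 − 26 = 58 mm. As written, the score is Response in every row.

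The first row is a caution. Summing alone turns Response into SD even when the second lesion is unchanged, so the summed column mixes dilution with growth. The clean comparison is with a non-target column: an unchanged lesion would be non-PD and the Response would stand, while unequivocal growth would be PD.

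**2. Compare with a new lesion.** Take the same patient and replace the growing old lesion with a new one. The table then gives PD whatever the target does.

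**3. Which endpoints move.**
- PFS, duration of response, duration of stable disease and duration of disease control all end at PD or death. A missing PD trigger can only lengthen them or leave them unchanged. It can also help a patient reach the 6-month mark for disease control.
- ORR needs CR or PR on two consecutive assessments at least 4 weeks apart. Growth after that does not remove the response. SAP 11.10.1 also counts a response that follows PD under continued treatment. So ORR changes only if the growth is present before confirmation and no qualifying response follows.

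**4. What one patient is worth.** Inputs: 2 responses in 10, an 80% interval of (5.5%, 45.0%) and a 5% no-interest rate (Protocol 15.6, SAP 6). The exact Clopper-Pearson limits with α = 0.20 are:
- lower = Beta quantile(α/2; x, n − x + 1)
- upper = Beta quantile(1 − α/2; x + 1, n − x)

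For x = 2, n = 10 this gives (5.45%, 44.96%), which reproduces the plan's figure. The Wald interval, 0.20 ± 1.2816 × √(0.2 × 0.8/10) = (3.8%, 36.2%), does not.

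For x = 1, n = 10 it gives (1.05%, 33.68%). The lower limit falls below 5%.

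One patient is 1/10 = 10 points of ORR if the denominator is 10. The SAP Efficacy population also includes run-in patients. If all of up to 6 run-in patients had locally advanced disease and the cohort of 10 filled (assumptions), one patient would be 1/16 = 6.25 points.

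**The case against.** Several stronger readings are tempting, and the documents do not support them.

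- **A reader might infer that the investigator is free to leave out any lesion.** That is not so. Every visible lesion that is also RECIST-measurable must be a target. Only lesions without a measurable imaging component can be left out.
- **A reader might infer that non-target growth is never PD.** Where the targets have a RECIST-measurable component, RECIST PD overrides in the combined clinical and RECIST table, and Appendix B counts non-target progression seen on imaging. The purely cutaneous lesion stays outside that route.
- **A reader might infer that the same lesion would be PD in the metastatic cohort.** Appendix B is limited to imaged non-skin or subcutaneous disease, so the documents do not show this.
- **A reader might infer that target choice by itself inflates ORR.** Omitted lesions could shrink more or less than chosen ones. Only the missing PD trigger has a clear direction.
- **A reader might take 2/10 as a go rule, or every patient with several lesions as misclassified.** The plan says only that further studies may be warranted, and SAP 10.5 has no formal testing. Misclassification also requires that a qualifying lesion was omitted and grew while the targets responded or were stable.

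It is also fair to say that part of Appendix C cannot be read. It cites a Section C on new skin lesions, and only A and B are in the text available. By its description it covers new rather than existing lesions, so it would probably not close the gap, but that cannot be confirmed. The missing column in the table is visible either way.

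These points narrow the concern. None of them supplies a scoring rule for an existing, purely cutaneous, non-target BCC.

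**Conclusion.** The point holds in limited form. In the text available, unequivocal growth of a non-target skin BCC that was present at baseline and has no RECIST-measurable component is not PD under Appendix C, and the patient can still be scored Response or SD. This is a stated scoring rule that gives a questionable result, because the same table treats any new lesion as PD.

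The direction is upward for PFS and for the response and disease-control durations. It is upward for ORR only when the growth precedes confirmation. The size cannot be estimated, because the documents do not give the number of patients with several qualifying lesions. The 2/10 to 1/10 shift shows how sensitive a cohort of 10 is to one rescored patient; it does not predict how many would be rescored.

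This is a worthwhile clarification, not a threat to the primary objective, which is the RP2D.

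**What to change.** 1. **Appendix C table.** Add a non-target column. For endpoint scoring, unequivocal progression of a non-target BCC that was present at baseline and measures 10 mm or more at the assessment is PD. Smaller lesions, as in Gorlin syndrome, do not count.
2. **Documentation.** At each tumor assessment, photograph and measure every visible BCC that at baseline was 10 mm or more and inoperable or contraindicated for surgery, whether or not it is a target. This should add no biopsies, which is a reason not to make all such lesions targets: Appendix C ties biopsies to target lesions.
3. **Surgery under exclusion criterion 2.** State how a non-target lesion that has been removed is handled in the score.
4. **SAP 11.9.1.** Repeat the rule, and say how it works with the 11.10.1 sentence that counts responses after PD.
5. **Data already collected.** List baseline non-target skin BCCs with their recorded course, and report a sensitivity ORR and PFS. Standardized photographs were required only for targets, so these data may be incomplete and the report should say so.
6. **Treatment.** The new PD category is for endpoint scoring. The sponsor should reconcile any effect on treatment continuation with Protocol 11.3.

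The cost is some appendix and SAP wording, a few more lesions to photograph and measure, and possibly a slightly less favourable ORR and PFS.

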APPENDIX D

DEFINITION OF WOMEN OF CHILDBEARING POTENTIAL AND ACCEPTABLE AND UNACCEPTABLE FORMS OF CONTRACEPTION

Women of childbearing potential are defined as follows:

- Patients with regular menses
- Patients with amenorrhea, irregular cycles, or using a contraceptive method that precludes withdrawal bleeding
- Women who have had a tubal ligation

Women are considered not to be of childbearing potential for the following reasons:

- The patient has undergone hysterectomy and/or bilateral oophorectomy.
- The patient is post-menopausal defined by amenorrhea for at least 1 year in a woman > 45 years old.
- Women of childbearing potential are required to use two forms of acceptable contraception, including one barrier method, during their participation in the study and for 6 months following discontinuation of CX-4945.

The following are acceptable forms of barrier contraception:

- Latex condom (always used with spermicide)
- Diaphragm (always used with spermicide)
- Cervical cap (always used with spermicide)

The following are acceptable forms of secondary contraception, when used with a barrier method:

- Tubal ligation
- Partner's vasectomy
- Hormonal contraception including birth control pills, patches, rings, or injections, with the exception of the progesterone-only "minipill"
- Intrauterine device (non–progesterone T)
- Vaginal sponge (containing spermicide)

In addition, 100% commitment to abstinence is considered an acceptable form of contraception.

The following are **unacceptable** forms of contraception for women of childbearing potential:

- IUD progesterone T
- Progesterone-only "minipill"
- Female condom
- Natural family planning (rhythm method) or breastfeeding
- Fertility awareness

Senhwa Biosciences, Inc.

- Withdrawal
- Cervical shield

APPENDIX E

VITAMIN D DOSING RECOMMENDATION¹

APPENDIX F

MEDICATIONS WITH THE POTENTIAL TO INTERACT WITH CX-4945

APPENDIX G

GUIDELINES FOR TISSUE BIOPSY IN PATIENTS WITH LOCALLY ADVANCED BASAL CELL CARCINOMA

Representative tumor biopsies are required for patients in the locally advanced basal cell carcinoma (BCC) cohort at the following timepoints:

- At screening, Week 8 and
- Either at the investigator's assessment of best clinical response or best clinical/RECIST response, if occurring prior to 24 weeks,

or

| Required Tumor Biopsy | Screening (Day -14 to -1) | Week 8 (± 3 Days) | Clinical Response if before Wk 24 | Week 24 (±3 Days) | At disease progression |
|---|------------------------------|-----------------------|---|-------------------------|---------------------------|
| Tumor biopsy for Hh pathway measurement (for laBCC patients in expansion cohort only) | Х | Х | | | |
| Tumor biopsy for tumor response assessment | Х | | Х | Х | X^1 |

At 24 weeks, if patient is still in study and is without evidence of progression

¹Recommended for all locally advanced BCC patients.

At any time during a patient's participation in the study, an optional tumor biopsy may be requested to clarify the response status of a patient. In addition, biopsy of any accessible target lesion(s) is highly recommended at the time of progression.

The sites, number, and technique of representative biopsies will be determined by the investigator on the basis of the size and location of the accessible lesions. It is recommended that any areas suspicious for residual disease be biopsied, as well as areas which appear to be free of disease. These biopsies will be reviewed by site's pathologist.

Two separate biopsies should be obtained rather than splitting the biopsies for response assessment and Hh pathway activity measurement.

For Hh pathway activity measurement, at least one and up to two punch biopsies of at least 4 mm in size, or 14-gauge or larger core needle biopsies should be obtained. It is recommended that approximately 0.1 cm³ of the tissue specimen, which should yield sufficient mRNA for this study. Tumor samples should immediately be snap frozen in

either liquid nitrogen or dry ice following surgical resection and stored at -80° C or below in a proper pre-cooled cryovial. It is highly recommended that biopsies should be snap frozen immediately and to be maintained frozen. Samples should be transported to Oncocyte Corporation per the "Sample Storage and Shipping Instructions" attached to this Guideline.

For tumor response assessment, at least one and up to five punch biopsies of at least 3 mm in size, or 14-gauge or larger core needle biopsies, as determined by the investigator, should be obtained. For large, accessible lesions in the skin and/or soft tissues, punch biopsies of 3 to 4 mm are strongly recommended to allow for optimal assessment of residual disease.

Biopsies for tumor response assessment should be fixed and paraffin embedded according to site standards.

The site pathologist's assessment will be used in the determination of response. The hematoxylin- and eosin-stained slides will be reviewed by site's pathologist to determine whether residual BCC is present. Epithelial rests or tumors consisting of epithelium with abnormal follicular differentiation, while not necessarily definitive evidence of residual BCC, will be interpreted as residual BCC.

If a biopsy obtained after administration of CX-4945 cannot be interpreted because of technical issues (e.g., crush artifact), then additional biopsies will be requested, if available.

Patients experiencing a clinical response whose biopsies show no evidence of residual BCC on biopsy will be considered to have a complete response; those experiencing a clinical response, but whose biopsies show evidence of residual BCC, will be considered to have a partial response.

Sample Storage and Shipping Instructions

(Refer to the most current version of the Pharmacodynamics Manual)

Tissue Biopsy Specimen Submission Form

(Refer to the most current version of the Pharmacodynamics Manual)

Specimen Shipment Notification Form

(Refer to the most current version of the Pharmacodynamics Manual)

